 - Preterm birth before 30 weeks: rate of delivery before 29+6 weeks
 - Preterm birth before 28 weeks: rate of delivery before 27+6 weeks
 - Birth weight: median weight (g) of the newborns at birth
 - Fetal or neonatal death: rate of intrauterine demise or neonatal death during the first 24 hours
 - Neonatal morbidity: rate of major adverse neonatal outcomes before discharge from the hospital
 - Intraventricular Haemorrhage (IVH): grades III-IV
 - Retinopathy of prematurity
 - Respiratory Distress Syndrome (RDS): grades II-IV,
 - Need for ventilation > 72 h
 - Necrotising enterocolitis
 - Proven or suspected sepsis, antibiotics (>5 days)
 - Need (Duration in days) for neonatal special care (NICU)
 - Harm from intervention
- Mother:
 - Maternal death
 - Significant maternal adverse events (rate):
 - Heavy bleeding: bleeding that requires a medical intervention
 - Cervical tear: cervical rupture due to the pessary placement
 - Uterine rupture: rupture of the uterus due to contractions or surgery
 - Physical or psychological intolerance to pessary: discomfort or pain due to the pessary that makes daily life uncomfortable (number of cases)
 - Rupture of membranes before 32 weeks: rate of–rupture of amniotic membranes before 31+6 weeks

[figure not shown]
- Infection/inflammation
- Hospitalisation for threatened preterm labour before 32 weeks: requirement of hospitalisation due to preterm contractions that need medical treatment to try to stop them before 31+6 weeks (rate)
 - Mean hospital stay duration: number of days of admittance at the hospital
 - Use of tocolytic treatment: Type of tocolytic, days of treatment, dose

4.2. Description of the trial design.

Open Multicentre International Collaborative Randomized Controlled Trial, in parallel groups, based on intention-to-treat analysis comparing the placement of a prophylactic cervical pessary with usual management in twin pregnancies with shortened cervix ≤ 25 percentile

4.3. Flowchart.

4.4. Description of the medical device and the treatment regimen.

The cervical pessary is a vaginal device (silicone ring) that is used to treat pregnant women for preventing spontaneous preterm birth. This device can be easily placed around the uterine cervix without pain (see annex I).

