A descriptive analysis by preterm birth will be carried out calculating means and medians for quantitative variables and proportions with 95% confidence intervals for categorical variables. In general, statistical comparisons with the pessary arm and the control arms or other group comparisons for primary and secondary outcomes will be performed with stratified tests as well as comparisons in the gestation subgroups. Events will be analysed for each twin and for single children assuming appropriate random effect regression models. Further subgroup analyses regarding the cervical length will be performed (e.g. CL 15 to 25mm and below 15mm). All tests, see also examples in the synopsis, will be two-sided using a significance level of $\alpha=0.05$.

For the primary endpoint we expect to have a drop out rate of up to 25% due to the long follow-up time (3 years) of the study; but we do not expect to have lost data for the secondary endpoints because for these parameters the study has a short follow-up time till time to birth only.

An interim analysis shall be conducted on key safety parameters after birth of 300 twins: the following safety endpoints will be assessed by a one-sided test with $\alpha=1\%$

- on level of the neonates: rate of preterm birth, time to birth, birth weight, death, neonatal morbidity, harm of intervention
- and on the maternal level: rate of hospitalisation for threatened preterm labour < 32 weeks, rate of PRoM <32 weeks, rate of infection / inflammation, rate of physical or psychological intolerance to pessary, rate of SAR/SAE, death.

The trial will be terminated as negative if a disadvantage for the pessary-treatment can be found in one of these tests. To guarantee a high safety level the significance level is chosen more conservatively than in a Bonferroni correction.

All analysis will be carried out with SPSS® version 19.0 or later (IBM Company SPSS Inc. Headquarters, Chicago, Illinois, USA) and R version 3.2.3 or later (R Foundation for Statistical Computing, Vienna, Austria).

Primary Outcome	Statistical Test
Children`s Long-Term Survival without Neuro-developmental Disability (3-Years-follow up)	Cochran-Mantel-Haenszel-Test, using 3 strata according to WoG
Secondary Outcome	Statistical Test
Birth before 34 Weeks of Gestation	Cochran-Mantel-Haenszel-Test, Chi-Quadrat Test
Time to Birth	Cox-Regression
Birthweight	van Elteren Test, Wilcoxon-Mann-Whitney Test
Fetal / Neonatal Death	Cochran-Mantel-Haenszel-Test, Chi-Quadrat Test

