Neonatal Morbidity	Cochran-Mantel-Haenszel-Test, Chi-Quadrat Test
Need for Hospitalization (mother)	Cochran-Mantel-Haenszel-Test, Chi-Quadrat Test
Days of Hospitalization (mother)	van Elteren Test, Wilcoxon-Mann-Whitney Test
Maternal Adverse Events	Cochran-Mantel-Haenszel-Test, Chi-Quadrat Test
Pessary Intolerance	Cochran-Mantel-Haenszel-Test, Chi-Quadrat Test
Vaginal Infections	Cochran-Mantel-Haenszel-Test, Chi-Quadrat Test

9.2. Expected number of subjects to be included.

For sample size calculation, we account for the stratified design and assume three equally large gestation groups. For the pessary group, we assume a combined event rate of at least 8% for the primary outcome and for the comparison of the pessary group with the control group we assume an odds ratio of 2.29. This odds ratio correspond to the lower bound of a one-sided confidence interval for the event rate given in van't Hooft (ProTwin Trial¹²). To reach a power of at least 80%, we have to evaluate at least 500 patients, 250 in the pessary group and 250 in the control group. To account for a drop out rate of 25%, overall n=672 pregnant women will be recruited.

9.3. Criteria for termination of the trial.

A non-justified case of maternal death (temporary stop until complete evaluation of the case by an external committee).

9.4. Selection of subjects to be included in each analysis.

The analysis will include all the subjects that have been randomised.

10. Direct Access to Data Source

Direct access will be granted to the authorized monitor, host institution and the regulatory authorities to permit trial-related monitoring, audits and inspections.

11. Quality and Control Assurance

Main investigator and collaborators: In order to ensure the Quality of the data they will provide instructions and training to the sites involved in the trial; review the CRF data; and detail of any other steps taken to ensure quality of research.

The main investigator will sign the study protocol and the “investigator’s commitment; he will apply for the Ethics Committee and the Director’s approval; and he will review the final report of the study.

The collaborators will assess patient’s eligibility, they will inform the patients and ask for the informed consent; and they will be responsible of the CRF and obtaining and registering all data.

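### Maternal hospital stay is defined as a mean number of days but is compared only by rank tests, with no between-arm estimate or confidence interval for mean days

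*Combined protocol and SAP*

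**What the plan says.** Section 4.1.2 lists among the maternal outcomes "Mean hospital stay duration: number of days of admittance at the hospital". The test table in section 9.1 gives the matching row, "Days of Hospitalization (mother", the entry "van Elteren Test, Wilcoxon-Mann-Whitney Test" and nothing else. The row just above it, "Need for Hospitalization (mother", tests admission yes or no with the Cochran-Mantel-Haenszel and chi-square tests.

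The text of section 9.1 plans a descriptive analysis "calculating means and medians for quantitative variables". Tests "will be two-sided using a significance level of" 0.05. Section 9.4 sets the population: "The analysis will include all the subjects that have been randomised". On completeness, section 9.1 says "we do not expect to have lost data for the secondary endpoints".

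The documents give no expected admission rate. They do not say how a woman with no admission is scored, or whether the stay for delivery counts.

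**The concern.** Neither planned test compares means. A rank test asks whether a woman drawn from one arm tends to have more days than a woman drawn from the other. That is a legitimate question, but it is not the one that section 4.1.2 names. The two can part company when an intervention changes how many women are admitted and how long they stay in opposite directions, or when it changes only the length of stay.

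The gap widens if many women have zero days. All zeros tie, so length of stay matters only in comparisons between two admitted women, and the rank test comes close to the admitted-or-not row. The report could then show a significant result for hospital days beside two nearly equal means, or a non-significant result beside clearly different means, with no prespecified estimate to settle it.

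**Working it through.** **Size of the check.** The documents give no figure for hospital days, so the planned sample size only fixes the numbers per arm. It reproduces. An 8% event rate with odds ratio 2.29 gives odds 0.08/0.92 × 2.29 = 0.199, a rate of 0.199/1.199 = 16.6%. A three-stratum Cochran-Mantel-Haenszel approximation with continuity correction at 250 + 250 has 79.8% power (83.4% without correction). For dropout, 500/6 rounds up to 84 per arm and stratum, 84/0.75 = 112, and 6 × 112 = 672. With no loss expected for secondary outcomes, each arm has 672/2 = 336 women.

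**Assumptions, not in the documents.** 30% of controls are admitted; stays are rounded-up exponential with a mean of about 6.5 days; women never admitted score 0.

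**Why zeros dominate the ranks.** The rank comparison rests on P(control longer) minus P(pessary longer) over all pairs of one woman per arm. With 20% (pessary) and 30% (control) admitted:

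- both zero, tied: 0.80 × 0.70 = 0.56
- only the control woman admitted: 0.80 × 0.30 = 0.24
- only the pessary woman admitted: 0.20 × 0.70 = 0.14
- both admitted: 0.20 × 0.30 = 0.06

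Length of stay decides at most 6% of pairs. Even if the pessary stay were longer in all of them, the balance would be 0.24 against 0.14 + 0.06 = 0.20, still pointing to fewer days with pessary. The mean per woman is p × m (share admitted times mean stay) and can move either way.

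**Overlap with the admission row.** With no true difference, the van Elteren statistic and the admitted-or-not Cochran-Mantel-Haenszel statistic correlate as follows (mean stay 8 days):

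| Share admitted | 15% | 30% | 50% | 70% | 90% |
|---|---|---|---|---|---|
| Correlation | 0.996 | 0.98 | 0.92 | 0.80 | 0.49 |

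**Rejection rates, two-sided 5%, 336 per arm.** The comparison of means is a Welch test.

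| Scenario (pessary vs control) | Mean days per woman | Rank test | Means |
|---|---|---|---|
| Strong offset: 20% × 9.5 vs 30% × 6.5 | 1.90 vs 1.95 | 76% | 6% |
| Mild offset: 27% × 7.2 vs 30% × 6.5 | 1.94 vs 1.95 | 12% | – |
| Longer stay only: 30% × 9.5 vs 30% × 6.5 | 2.85 vs 1.95 (+46%) | 9% | 53% |
| Fewer admissions only: 20% × 6.5 vs 30% × 6.5 | 1.30 vs 1.95 (−33%) | 84% | 54% |
| Strong offset, plus about 4 delivery days for all | 5.90 vs 5.95 | 29% | 6% |
| Longer stay, plus about 4 delivery days for all | 6.85 vs 5.95 | 10% | 51% |

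Other runs of the same scenarios gave 74% for the strong offset, 11% for the mild one, and 8% against 56% for the longer stay. Both methods held their level with no difference (5.2% and 5.5%).

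**A different stay model.** With overdispersed counts, the van Elteren test and exactly equal means, 20% × 12 against 30% × 8 days (2.4 in both arms) gave 70.9%, or 58.2% at about 250 per arm. Further equal-mean cases gave 43.8% (10% vs 15% admitted), 42.4% (40% vs 50%), 21.2% (25% vs 30%) and 21.3% (70% vs 80%). Halving the stay from 8 to 4 days at 30% admission was detected in 18.2% by van Elteren and 98.7% by means.

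**The case against.** The rank test is a conventional and valid choice for skewed days. In the strong-offset scenario the two distributions really do differ, so rejecting is correct for the hypothesis that the test addresses. The plan does the same for birth weight, which it summarises by a median and tests by ranks. Means and admission rates will also be reported, so a reader could see a discrepancy. This stands, and it is why the rank test should stay.

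A reader might infer that most women will have zero days, so that the row merely repeats the admission test. The documents do not establish this. Neither the outcome definition nor the table row names a cause of admission, and the list layout does not settle whether the stay belongs to threatened preterm labour. Section 9.4 says who is analysed, not how they are scored. If delivery stays count, or only admitted women are analysed, there are few or no zeros. Among about 100 admitted women per arm, the rank test detects the longer stay in 69% of trials against 81% for means. With heavy-tailed (lognormal) stays it does better than means, 57% against 37%. An admitted-only analysis would, however, compare groups formed after randomisation.

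A reader might also infer that the trial would usually credit the pessary wrongly. The 76% needs a cut of one third in admissions, offset almost exactly by a 46% longer stay. That is a constructed case, and milder offsets give about 12% to 21%.

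Nor do the results support replacing the rank test by a test of means. When admissions fall and the stay is unchanged, means lose power: 54% against 84%, and 37% against 86% with lognormal stays.

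Finally, no decision rests on this row. It is one of many secondary outcomes, and the interim safety list uses the rate of hospitalisation, not days.

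**Conclusion.** The mismatch between definition and analysis is in the text and needs no assumption: a mean is named, only rank tests are assigned, and no between-arm estimate or interval for mean days is planned. Adding delivery days for everyone weakens the disagreement but does not remove it (29% against 6%, and 10% against 51%).

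Its size rests on assumed admission rates and stays. The range is about 12% to 76% rejections at near-equal means, and about 9% detection of a 46% rise in mean days. Near-duplication of the admission row holds if about half or more of the women have zero days, and fades as admission becomes common. This is a cheap improvement to a secondary outcome and does not affect the primary analysis.

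**What to change.** For the row "Days of Hospitalization (mother":

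- Add the difference in mean days per randomised woman, 0 if never admitted, stratified by gestation group: Δ = Σ w_h × (pessary mean − control mean in group h), with w_h the share of women in group h. Give a bootstrap 95% confidence interval, resampling women within arm and gestation group.
- State in section 4.1.2 whether the delivery admission counts.
- Base any statement about mean or total hospital days on this estimate.
- Keep the van Elteren test, described as a test of a distributional difference.

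The cost is one table row, a line or two of definition and a few lines of R, which section 9.1 already names. If the delivery stay is left out, the case report form must record it separately; the documents do not show whether it does.

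The downside is that a mean is sensitive to a few long stays, and its interval is less sensitive than the rank test when the pessary only reduces admissions (about 54% against 84% under the assumed rates). That effect already has its own test in the row "Need for Hospitalization (mother". The bootstrap interval itself was not simulated; the figures for means come from the Welch comparison.

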13.1. Data ownership

Sponsor and participating Center have expressly agreed that any and all data collected and prepared in the context of the study shall be the property of the Sponsor, provided that participating Center shall remain the owner of its source data and may utilize such data as it deems appropriate without the approval, but with the reliable communication of Sponsor. Furthermore, Sponsor will always have access to the Study data, in terms of good faith and cooperation, in order to improve their own knowledge and information.

14. Funds and Insurance

According to German legislation and Ethical Committee decisions, it is not necessary to enter into an insurance contract in order to cover patients while using this medical device in a clinical trial. Insofar as it has been issued with the appropriate certificate of the State Medicines Agency to the concrete use of the medical device.

Nevertheless, it will be mandatory to enter into a hedging insurance by any other participating centre of this clinical trial, in the case that it is mandatory according to the laws of their country.

No funding is provided for the study.

15. Publication policy

The Sponsor takes the commitment of publishing the results of the study; despite they are good or bad.

Promoter and participating Centre agree that publications or presentations of any of the results from the study shall be in accordance with accepted scientific practice, academic standards and customs.

Authorship and other related publications questions shall be addressed in accordance with the principles of the 'Uniform Requirements for Manuscripts Submitted to Biomedical Journals' and in accordance with the requirements of the respective medical journal.

Sponsor agrees to ensure co-authorship for clinical co-investigators on any proposed multicentre publication.

Sponsor and participating Centres agree that at first they will strive to make a joint publication. After such joint publication or one year after termination of the study the following shall be agreed:

Annex I. Technical details of the device.

The Arabin cervical pessary

CE-certified for preventing spontaneous preterm birth (CE 0482 / EN ISO 13485: 2012 + AC:2012 annex III of the council directive 93/42 EEC).

This pessary is used to treat pregnant women with cervical incompetence in order to support the cervix and sacralise it towards the sacrum.

It may be indicated in pregnancies with a history of premature labour, multiple pregnancies or mothers who are exposed to physical strain (e.g. standing for a long time). It may also be indicated in pregnant women suffering from prolapse of the genital organs.

The cerclage pessary can easily be folded and inserted without pain.

In general, cerclage pessaries should have a height of 21-25 mm in singleton pregnancies and a height of 25-30 mm in multiple pregnancies or pregnant patients with complaints of prolapse. The width of the upper and lower diameter should be chosen depending on the individual constitution of the pregnant patient.

Cerclage pessaries can be ordered in a non-perforated or perforated version. The perforations facilitate discharge to pass.

Sizes and Models: Cerclage pessaries are classified according to

- The lower larger diameter (65 or 70 mm)
- The height (17, 21, 25, 30 mm)
- The upper smaller diameter (32 or 35 mm)

[name] online shop. <http://www.dr-arabin.de/e/cerclage.html>
